MRI	xx (xx.x%)				
Other	xx (xx.x%)				
No	xx (xx.x%)				
Joint(s)/Area(s) investigated:					
Shoulder	xx (xx.x%)	xx(xx.x%)	xx (xx.x%)	xx (xx.x%)	xx (xx.x%)
Elbow	xx (xx.x%)				
Hip	xx (xx.x%)				
Knee	xx (xx.x%)				
Ankle	xx (xx.x%)				
Spine	xx (xx.x%)				

Final 1.0 | 12-Jul-2023 | Page 15 of 205

Hands	xx (xx.x%)	xx (xx.x%)	xx (xx.x%)	xx (xx.x%)	xx(xx.x%)
Feet	xx (xx.x%)	xx(xx.x%)	xx (xx.x%)	xx (xx.x%)	xx(xx.x%)
Other	xx (xx.x%)	xx (xx.x%)	xx (xx.x%)	xx (xx.x%)	xx (xx.x%)
Osteoarthritis radiologically significant					
Yes	xx (xx.x%)	xx(xx.x%)	xx(xx.x%)	xx (xx.x%)	xx(xx.x%)
No	xx(xx.x%)	xx (xx.x%)	xx (xx.x%)	xx (xx.x%)	xx (xx.x%)
Kellgren-Lawrence score reported					
Yes	xx (xx.x%)	xx(xx.x%)	xx(xx.x%)	xx(xx.x%)	xx(xx.x%)
Grade 0	xx (xx.x%)	xx(xx.x%)	xx(xx.x%)	xx(xx.x%)	xx(xx.x%)
Grade 1	xx (xx.x%)	xx (xx.x%)	xx (xx.x%)	xx (xx.x%)	xx (xx.x%)
Grade 2	xx (xx.x%)	xx(xx.x%)	xx(xx.x%)	xx(xx.x%)	xx(xx.x%)
Grade 3	xx (xx.x%)	xx(xx.x%)	xx (xx.x%)	xx (xx.x%)	xx(xx.x%)
Grade 4	xx (xx.x%)	xx(xx.x%)	xx (xx.x%)	xx (xx.x%)	xx(xx.x%)
No/Not applicable	xx(xx.x%)	xx (xx.x%)	xx (xx.x%)	xx (xx.x%)	xx (xx.x%)
Radiologic Scoring System Used?					
Yes	xx (xx.x%)	xx(xx.x%)	xx(xx.x%)	xx(xx.x%)	xx(xx.x%)
No	xx (xx.x%)	xx (xx.x%)	xx (xx.x%)	xx (xx.x%)	xx (xx.x%)
Grade 2 Grade 3 Grade 4 No/Not applicable Radiologic Scoring System Used? Yes	xx (xx.x%) xx (xx.x%) xx (xx.x%) xx (xx.x%)	xx (xx.x%) xx (xx.x%) xx (xx.x%) xx (xx.x%) xx (xx.x%)			

MRI = magnetic resonance imaging; N = number of subjects per treatment group.

Programming Notes:

- Display only Joint(s)/Areas(s) affected and investigated with non-missing value.
- A column for column dosing (column for column for col

^[1] Subjects who reported more than one radiologic investigation within each category were only counted once. Reference Listing: 16.2.4.3

[figure not shown]

Table 14.1.5.2 Osteoarthritis Characteristics Safety Population

Programming Notes:

- Same shell as Table 14.1.5.1.
- Display only Joint(s)/Areas(s) affected and investigated with non-missing value.
- A column for column

Table 14.1.5.3 Osteoarthritis Characteristics mITT Population

Programming Notes:

- Same shell as Table 14.1.5.1.
- Display only Joint(s)/Areas(s) affected and investigated with non-missing value.
- A column for column for column dosing (column dosing (column for column for

Table 14.1.5.4 Osteoarthritis Characteristics PK Population

Programming Notes:

- Same shell as Table 14.1.5.1.
- Display only Joint(s)/Areas(s) affected and investigated with non-missing value.
- A column for column dosing (column for column for col

Final 1.0 | 12-Jul-2023 | Page 17 of 205

[figure not shown]

Table 14.1.6

Medical History by System Organ Class and Preferred Term
Safety Population

System Organ Class	Placebo		MEDI7352				
Preferred Term	(N=xxx)	CCI (N=xx)	(N=xx)	(N=xx)	(N=xxx)		
Any Medical History	xx (xx.x %)	xx (xx.x %)	xx (xx.x %)	xx (xx.x %)	xx (xx.x %)		
System Organ Class 1	xx (xx.x %)	xx (xx.x %)	xx (xx.x %)	xx (xx.x %)	xx (xx.x %)		
Preferred Term 1	xx (xx.x %)	xx (xx.x %)	xx (xx.x %)	xx (xx.x %)	xx (xx.x %)		
Preferred Term n	xx (xx.x %)	xx (xx.x %)	xx (xx.x %)	xx (xx.x %)	xx (xx.x %)		
System Organ Class n	xx (xx.x %)	xx (xx.x %)	xx (xx.x %)	xx (xx.x %)	xx (xx.x %)		
Preferred Term 1	xx (xx.x %)	xx (xx.x %)	xx (xx.x %)	xx (xx.x %)	xx (xx.x %)		
Preferred Term n	xx (xx.x %)	xx (xx.x %)	xx (xx.x %)	xx (xx.x %)	xx (xx.x %)		

N = number of subjects per treatment group.

Note: All medical history terms were coded using the Medical Dictionary for Regulatory Activities (MedDRA), version 26.0. At each level of summarization (system organ class or preferred term), subjects having more than one medical history term were counted only once. System organ class and preferred terms are sorted in descending order of frequency of Total column, and alphabetically if same frequency.

Reference Listing: 16.2.4.2

Programming Notes:

- SOC and PT texts should be in proper case in table.
- Sort SOC and PT (within SOC) in descending order of frequency in the Total column. Sort alphabetically in case of ties.
- Uncoded Medical History Events
 - O When there are uncoded Medical History Events in the database, the events will be summarized with SOC and PT set to [Not Coded]. The [Not Coded] will be sorted at the end of the table.
- A column for column

Final 1.0 | 12-Jul-2023 | Page 18 of 205

Table 14.1.7
Prior Medications by ATC Class and Preferred Name
Safety Population

ATC Class [1]	Placebo		MEDI7352		Total
Preferred Term	(N=xx)	CCI (N=xx)	(N=xx)	(N=xx)	(N=xx)
Subjects with at Least One Prior Medication	xx (xx.x%)	xx (xx.x%)	xx (xx.x%)	xx (xx.x%)	xx (xx.x%)
ATC Level 2 1	xx (xx.x%)	xx (xx.x%)	xx (xx.x%)	xx (xx.x%)	xx (xx.x%)
Preferred Name 1	xx (xx.x%)	xx(xx.x%)	xx(xx.x%)	xx (xx.x%)	xx (xx.x%)
Preferred Name n	xx (xx.x%)	xx (xx.x%)	xx (xx.x%)	xx (xx.x%)	xx (xx.x%)
ATC Level 2 n	xx (xx.x%)	xx (xx.x%)	xx (xx.x%)	xx (xx.x%)	xx (xx.x%)
Preferred Name 1	xx(xx.x%)	xx(xx.x%)	xx(xx.x%)	xx (xx.x%)	xx (xx.x%)
Preferred Name n	xx(xx.x%)	xx(xx.x%)	xx(xx.x%)	xx (xx.x%)	xx (xx.x%)

ATC = Anatomical Therapeutic Class; N = number of subjects per treatment group.

Note: Prior medications are defined as medications that started before first dose of study, whether they were stopped before first dose of study medication or not. All prior medications are coded using WHO drug dictionary version vMar2023. At each level of summarization (ATC Level 2 or Preferred Name), subjects who reported more than one prior medication were only counted once. ATC Level 2 and Preferred Term are sorted in in descending order of frequency of total, and alphabetically if same frequency.

Reference Listing: 16.2.9.16

Programming Notes:

- If uncoded ATC Level or Preferred Name, please put them as [Not Coded]
- ATC and Preferred Name texts should be in proper case in table.
- A column for column dosing (column dosing (column dosing (column dosing (column dosing dosing dosing (column dosing dos

Final 1.0 | 12-Jul-2023 | Page 19 of 205

^[1] ATC Class is defined as ATC Level 2.

[figure not shown]

Table 14.1.8 Protocol Deviations Safety Population

	Placebo	MEDI7352			Total	
	(N=xx)	(N=xx)	(N=xx)	(N=xx)	(N=xx)	
Subjects With Any Important Protocol Deviation/Violation	xx (xx.x%)					
Protocol Deviation Type 1	xx (xx.x%)					
Protocol Deviation Type 2	xx (xx.x%)	xx(xx.x%)	xx (xx.x%)	xx(xx.x%)	xx (xx.x%)	
Protocol Deviation Type 3	xx(xx.x%)	xx(xx.x%)	xx(xx.x%)	xx(xx.x%)	xx (xx.x%)	
Protocol Deviation Type 4	xx (xx.x%)					
Protocol Deviation Type 5	xx (xx.x%)	xx(xx.x%)	xx (xx.x%)	xx(xx.x%)	xx (xx.x%)	
Protocol Deviation Type 6	xx (xx.x%)	xx (xx.x%)	xx (xx.x%)	xx(xx.x%)	xx (xx.x%)	

N = number of subjects per treatment group.

Notes: Percentages are n/Number of subjects by treatment group*100.

[figure not shown]
Subjects with one or more deviations within a type of protocol deviation were counted only once.

Reference Listing 16.2.2.1

Programming Notes:

• A column for column for dosing (column for dosing

Final 1.0 | 12-Jul-2023 | Page 20 of 205

2. Exposure and Compliance

Table 14.1.9
Overall Study Drug Exposure
Safety Population

[figure not shown]
	Placebo	MEDI7352			Total
Category/ Statistic	(N=xx)	(N=xx)	(N=xx)	(N=xx)	(N=xx)
Maximum Number of Doses Administered [1]					
1 Dose	xx (xx.x%)	xx (xx.x%)	xx (xx.x%)	xx (xx.x%)	xx (xx.x%)
2 Doses	xx (xx.x%)	xx (xx.x%)	xx (xx.x%)	xx (xx.x%)	xx (xx.x%)
3 Doses	xx (xx.x%)	xx (xx.x%)	xx (xx.x%)	xx (xx.x%)	xx (xx.x%)
4 Doses	xx (xx.x%)	xx (xx.x%)	xx (xx.x%)	xx(xx.x%)	xx (xx.x%)
5 Doses	xx (xx.x%)	xx (xx.x%)	xx (xx.x%)	xx(xx.x%)	xx (xx.x%)
6 Doses	xx (xx.x%)	xx (xx.x%)	xx (xx.x%)	xx (xx.x%)	xx (xx.x%)
Total Duration of Exposure (days) [2]					
n	XX	XX	XX	XX	XX
Mean (SD)	xx.x(xx.xx)	xx.x(xx.xx)	xx.x(xx.xx)	xx.x(xx.xx)	xx.x(xx.xx)
Median	XX.X	XX.X	XX.X	XX.X	XX.X
Q1, Q3	XX.X, XX.X	XX.X, XX.X	XX.X, XX.X	XX.X, XX.X	XX.X, XX.X
Min, Max	XX, XX	xx, xx	xx, xx	xx, xx	XX, XX
Total (cumulative) dose infused (mL)					
n	XX	XX	XX	XX	XX
Mean (SD)	xx.x(xx.xx)	xx.x (xx.xx)	xx.x (xx.xx)	xx.x (xx.xx)	xx.x (xx.xx)
Median	XX.X	XX.X	XX.X	XX.X	XX.X
Q1, Q3	XX.X, XX.X	XX.X, XX.X	XX.X, XX.X	XX.X, XX.X	XX.X, XX.X
Min, Max	xx, xx	XX, XX	XX, XX	xx, xx	xx, xx

n = number of subjects by treatment group with collected parameter; N = number of subjects per treatment group; SD = standard deviation; Q1 = first quartile; Q3 = third quartile.

Final 1.0 | 12-Jul-2023 | Page 21 of 205

^[1] Subjects are counted once for each level of dose administered.

^[2] Duration of exposure (days) = min(date of last dose of treatment + 14 days or date of death) – date of first dose of treatment + 1. Reference Listing: 16.2.5.1

[figure not shown]

Programming Notes:

- Add all categories even if count is 0.
- A column for column

Final 1.0 | 12-Jul-2023 | Page 22 of 205

3. Primary Efficacy Analysis

Table 14.2.1.1.1

Daily Pain NRS: Summary Statistics (Observed Cases)

mITT Population

	Placebo		MEDI7352		Total
Visit/ Statistic	(N=xx)	CCI (N=xx)	(N=xx)	(N=xx)	(N=XX)
Baseline [1]					
n	XX	XX	XX	XX	XX
Mean (SD)	xx.x (xx.xx)	xx.x (xx.xx)	xx.x (xx.xx)	xx.x (xx.xx)	xx.x (xx.xx)
Median	XX.X	XX.X	XX.X	XX.X	xx.x
Q1, Q3	XX.X, XX.X	XX.X, XX.X	XX.X, XX.X	XX.X, XX.X	XX.X, XX.X
Min, Max	XX, XX	XX, XX	xx, xx	xx, xx	xx, xx
Week 2					
n	XX	XX	XX	XX	XX
Mean (SD)	xx.x (xx.xx)	xx.x(xx.xx)	xx.x(xx.xx)	xx.x(xx.xx)	xx.x (xx.xx)
Median	XX.X	XX.X	XX.X	XX.X	XX.X
Q1, Q3	XX.X, XX.X	XX.X, XX.X	XX.X, XX.X	XX.X, XX.X	XX.X, XX.X
Min, Max	xx, xx	XX, XX	xx, xx	XX, XX	xx, xx
Week 2 CFB					
n	XX	XX	XX	XX	XX
Mean (SD)	xx.x (xx.xx)	xx.x(xx.xx)	xx.x(xx.xx)	xx.x(xx.xx)	xx.x (xx.xx)
Median	xx.x	XX.X	XX.X	XX.X	xx.x
Q1, Q3	XX.X, XX.X	XX.X, XX.X	XX.X, XX.X	XX.X, XX.X	XX.X, XX.X
Min, Max	xx, xx	XX, XX	xx, xx	XX, XX	XX, XX

[figure not shown]

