8 STATISTICAL APPENDIX

- A1. Bayesian linear model to calculate posterior probabilities of the maximum treatment effect (CCI versus Placebo data) using **bFitMod** function within **DoseFinding** package
 - Calculate the Least Squares Means for each dose group and their variancecovariance matrix (using package 'emmeans')
 - Create indicator variable for dose: 0=Placebo and 1=CC
 - Execute **bFitMod** with:
 - a. model as "linear"
 - b. Independent Gaussian Priors for intercept and slope parameters: N(0,100). With starting values of 0.
 - c. Lsmean Estimates and Variance-Covariance for placebo and column as inputs from the ANCOVA described in section 6.1.5, and
 - d. simulate 100,000 draws from the posterior distribution, with seed = 301020 (to allow for independent replication).
 - e. Process the saved **bFitMod** object as follows:
 - Select the 'samples' element from the saved bFitMod object
 - The 'delta' variable within the 'samples' element is the posterior value of the treatment difference between CCI and placebo
 - Estimate the posterior probabilities that the treatment effect is
 - a. Greater than zero

b. Greater than a 1.25-point reduction from the posterior sample of the slope parameter.

by computing the proportion of posterior 'delta' values less than zero and -1.25, respectively.

A2. Simulation of Conditional Power of the Dose Response Curve test under original stage 4 sample size and dose allocation

- There is no formula available to compute conditional power of the dose response test, therefore a simulation approach will be taken as follows:
- Calculate the residual standard deviation (RMSE) from the ANCOVA model fitted to the interim data.
- Simulate the stage 4 data for each of the four dose groups from an emax model with an appropriate ED50 and random error = residual standard deviation.

The parameters for the emax model, from which to simulate from, will be calculated (fixed) as follows:

```
ED50 = 450*(Y_{IA}-Y_{450})/(Y_{450}-450*Y_{IA}/150) and 
emax = Y_{450}*(ED_{50}+450)/450
```

where Y_{IA} = observed effect of CCI versus placebo, Y_{450} = one of the two scenarios of the CCI effect versus placebo.

If the estimated ED50 is negative then the data are not consistent with an Emax model therefore linear interpolation between zero and CCI will be used instead of an Emax approach for estimating the effect of the CCI dose in stage 4 as follows: Lsmean for CCI versus placebo = (CCI)*Lsmean CCI versus placebo .

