2. Equations for Dose (ED_P) to achieve a certain proportion P of the effect of the maximum dose studied versus placebo (See DoseFinding manual page 51 where ED is 'Effective Dose')

Statistical Analysis Plan, Sponsor AstraZeneca Protocol Number D5680C00002 PCN Number MEDU177093

Emax:
$$ED_P = (P * ED_{50}*max(doses))/(ED_{50}+(1-P)*max(doses)) = (P * ED_{50}*150)/(ED_{50}+(1-P)*150)$$

Exponential: $ED_P = \delta *log((P*exp(max(doses)/\delta) + 1-P)) = \delta *log((P*exp(150/\delta) + 1-P))$
(The function ED from the DoseFinding package will be used for the above)

3. Equation for Dose (asym $ED_{\underline{P}}$) to achieve a certain proportion P of the asymptotic maximum effect (E_{max}) versus placebo

Emax: asymptotic $ED_P = (P*ED_{50})/(1-P)$

Simulation-based CI will be created for each of the above quantities from the mean and covariance matrix of the model parameters, assuming multivariate normality. Therefore 10,000 samples from the multivariate distribution will be taken, and for each simulation the TD and ED estimates calculated. The 2.5% and 97.5% percentiles will then form the appropriate 95% two-sided CI.

Statistical Analysis Plan

[figure not shown]
Sponsor	AstraZeneca
Protocol Title:	A Randomised, Double-Blind, Placebo-Controlled, Dose- Response Study of the Efficacy and Safety of MEDI7352 in Subjects with Painful Diabetic Neuropathy
Development Phase	2
Protocol Number:	D5680C00002
Premier Research PCN:	MEDU177093
Document Version:	Final Version 1.1
Document Date:	31-Aug-2023

Approvals

Role	Signatures
	Print Name: PPD Biostatistician, Premier Research
Biostatistician	Sign Name: PPD
	Print Name: PPD PPD Biostatistics, Premier Research
Peer Reviewer	Sign Name: PPD

[figure not shown]
Role	Signatures	
	Print Name: PPD Statistical Consultant to AstraZeneca	
AstraZeneca Biostatistician	Sign Name: PPD	
	Print Name: PPD	
	AstraZeneca Neuroscience	
AstraZeneca Representative	Sign Name: PPD	

Document History

Version	Date	Author	Description
0.1	27-Mar-2019	PPD	Draft Version
0.2	16-Apr-2021	PPD	Draft Version
0.3	25-Jun-2021	PPD	Draft Version
0.4	24-Mar-2023	PPD	Draft Version
0.5	21-Apr-2023	PPD	Draft Version
0.6	24-May-2023	PPD	Draft Version
1.0	12-Jul-2023	PPD	Final Version
1.1	31-Jul-2023	PPD	Final Version

[figure not shown]
Page 4 of 54

Table of Contents

Approvals	1
Document History	3
Table of Contents	4
List of Tables	6
List of Figures	6
List of Abbreviations.	7
1. Overview	11
2. Study Objectives and Endpoints	11

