2. Equations for Dose (ED_P) to achieve a certain proportion P of the effect of the maximum dose studied versus placebo (See DoseFinding manual page 51 where ED is 'Effective Dose')

Emax: $ED_P = (P * ED_{50} * max(doses))/(ED_{50} + (1-P) * max(doses)) = (P * ED_{50} * 150)/(ED_{50} + (1-P) * 150)$

[figure not shown]
Exponential: $ED_P = \delta * log((P*exp(max(doses)/\delta) + 1-P)) = \delta * log((P*exp(150/\delta) + 1-P))$

(The function ED from the DoseFinding package will be used for the above)

3. Equation for Dose (asym ED_P) to achieve a certain proportion P of the asymptotic maximum effect (E_{max}) versus placebo

Emax: asymptotic $ED_P = (P*ED_{50})/(1-P)$

Simulation-based CI will be created for each of the above quantities from the mean and covariance matrix of the model parameters, assuming multivariate normality. Therefore 10,000 samples from the multivariate distribution will be taken, and for each simulation the TD and ED estimates calculated. The 2.5% and 97.5% percentiles will then form the appropriate 95% two-sided CI.

[figure not shown]

Sponsor:	AstraZeneca
Protocol Title	A Randomised, Double-Blind, Placebo-Controlled, Dose- Response Study of the Efficacy and Safety of MEDI7352 in Subjects with Painful Diabetic Neuropathy
Development Phase	2
Protocol Numbers:	D5680C00002
Premier Research PCNs:	MEDU177093
Document Version:	Final Version 1.0
Document Date:	12-Jul-2023

Document History

Version	Date	Author	Description
0.1	24-Mar-2023	PPD	Draft Version
0.2	21-Apr-2023	PPD	Draft Version
0.3	24-May-2023	PPD	Draft Version
0.4	20-Jun-2023	PPD	Draft Version

Final 1.0 | 12-Jul-2023 | Page 1 of 205

Tables, Listings, and Figures Conventions

All listings, tables, and graphs will have a header showing the sponsor company name, protocol and version of delivery and a footer showing the version of SAS, the file name and path, and the source of the data (listing number).

The following reporting conventions will be adopted for the presentation of study data. These conventions will enhance the review process and help to standardize the presentation with common notations.

[figure not shown]
General Reporting Conventions

- All tables and data listings will be developed in landscape orientation.
- Specialized text styles, such as bolding, italics, borders, shading, and superscripted and subscripted text will not be used in tables, figures, and data listings unless they add significant value to the table, figure, or data listing.

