'MOD' step [3] Selected Model xxxxxxxxx

Parameter	Estimate	95% CI of Estimate [6]
ED50	XX.X	[x.xx to x.xx]
ED90 [4]	XX.X	[x.xx to x.xx]
Asymptotic ED90 [5]	XX.X	[x.xx to x.xx]
Dose to achieve target (-1.25) effect	XX.X	[x.xx to x.xx]
Treatment effect at dose = 5 mcg	XX.X	[x.xx to x.xx]
Treatment effect at dose = 50 mcg	XX.X	[x.xx to x.xx]
Treatment effect at dose = 150 mcg	XX.X	[x.xx to x.xx]
Treatment effect at dose = 450 mcg	xx.x	[x.xx to x.xx]

CI: Confidence Interval; LOCF = Last Observation Carried Forward; MCP = Multiple Comparisons; Procedure; MOD = Modelling; NRS = Numeric rating scale.

Programming Notes:

• The 'MOD' step will only be performed if stage 4 is initiated, otherwise there would be insufficient dosing data to fit the non-linear models.

Final 1.0 | 12-Jul-2023 | Page 27 of 205

^[3] Results from the 'MOD' step will only be available in case any of the MCP tests is statistically significant.

^[4] ED90 = Effective Dose giving 90% of the effect of the maximum dose studied.

^[5] Asymptotic ED90 = Effective Dose giving 90% of the asymptotic maximum effect.

^{[6] 2.5%} and 97.5% quantiles taken from 100000 samples from the multivariate normal distribution for model fitted estimates and its covariance matrix. Reference Listing: 16.2.6.1

[figure not shown]

Table 14.2.1.2.2 Statistical Analysis of CFB to Week 12 Daily Pain NRS: Primary ANCOVA Analysis (LOCF) mITT Population

Model parameter estimates

					2-sided 95% unadjusted Asymmetric CL		2-sided
Parameter	Estimate	t value	Degrees of freedom	Standard Error	CL	[1]	P-value [2]
Intercept	XX.XX	XX.XX	•	xx.xxx	[x.xx to x.xx]		
Co-Medication Type			2				0.xxxx
Baseline pain NRS	XX.XX	XX.XX	1	XX.XXX	[x.xx to x.xx]		0.xxxx
Active 5 mcg vs Placebo	XX.XX	XX.XX	1	XX.XXX	[x.xx to x.xx]	[x.xx to x.xx]	0.xxxx
Active 150 mcg vs Placebo	XX.XX	XX.XX	1	XX.XXX	[x.xx to x.xx]	[x.xx to x.xx]	0.xxxx
Active 450 mcg vs Placebo	XX.XX	XX.XX	1	XX.XXX	[x.xx to x.xx]	[x.xx to x.xx]	0.xxxx
Model residual standard deviation	XX.XX						

ANCOVA = analysis of covariance; CFB = Change from Baseline;

CL = Confidence limits; LOCF = Last Observation Carried Forward; NRS = Numeric rating scale.

[2] P-value is derived from the following model: ANCOVA by dose using NRS baseline value and co-medication as covariates, with CFB to Week 12 (LOCF) as dependent variable.

Least Square Means

Treatment	Number of Subjects	LS mean [3]	95% CI of LS mean
Active 450 mcg	XX	X.XX	[x.xx to x.xx]
Active 150 mcg	XX	X.XX	[x.xx to x.xx]

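### SAP Section 15 sets the maximum dose to 150 in its printed ED_P formulas although 450 µg/kg is the highest dose shown, so ED90 or its interval is understated if that constant is coded

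*SAP*

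**What the plan says.** SAP v1.1, Section 15, item 2 describes ED_P as the dose "to achieve a certain proportion P of the effect of the maximum dose studied versus placebo". For the Emax model it first writes the solution with max(doses), then continues the same line with a number in its place: "P * ED_{50} * 150)/(ED_{50} + (1-P) * 150". The exponential line ends the same way: "\delta * log((P*exp(150/\delta) + 1-P". SAP v1.0 prints the same constant: "P * ED_{50}*150)/(ED_{50}+(1-P)*150".

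Below the equations the section adds: "The function ED from the DoseFinding package will be used for the above". It then specifies simulation-based intervals. Model parameters are drawn 10,000 times from a multivariate normal distribution, TD and ED are calculated for each draw, and the 2.5% and 97.5% percentiles are taken.

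The table that receives these results is shell Table 14.2.1.2.1. Its footnote 4 reads "ED90 = Effective Dose giving 90% of the effect of the maximum dose studied", and its MOD block contains the row "Treatment effect at dose = 450 mcg". The interim plan, appendix A2, parameterises its Emax curve as "ED50 = 450*(Y_{IA}-Y_{450})/(Y_{450}-450*Y_{IA}/150", with 450 as the upper of two doses.

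**The concern.** Label, general formula and output footnote all refer to the highest dose studied, but the worked expression uses 150. On the document's own evidence 150 is not the highest dose. A program written from the printed expression would give the dose reaching 90% of the 150 µg/kg effect and report it as 90% of the maximum-dose effect.

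ED90 is one of the parameters that Section 8.1 lists for the MOD step, and it serves the secondary dose-response objective. A value capped by the wrong reference dose would make the curve look more potent than the fit says. A point estimate and an interval coded from different constants would contradict each other in one table row.

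**Working it through.** **Which dose is the maximum?** These places are legible despite the redactions:
- Shell Table 14.2.1.2.1, MOD block: effects at 5, 50, 150 and 450.
- Shell Table 14.2.1.2.2 (ANCOVA) and the MMRM shells: rows for 5, 150 and 450.
- Shell Figure 14.2.1.2: dose axis 0, 5, 150, 450 µg/kg.
- Interim plan A2: Y_450 stands for the two effect scenarios. The same appendix assigns the Section 6.1.6 scenario values to the highest stage 4 dose.

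These shells are v1.0, because the v1.1 shells at hand stop before these tables. SAP v1.0 carries the same 150, so the v1.0 set is inconsistent in any case.

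The power statement cannot settle the question. With n = 81, 37, 51 and 67, SD 2.4, a difference of 1.25 at the top dose and one-sided 0.025, assumed doses of 0, 50, 150 and 450 give power of 87.4% to 94.7% for ED50 from 1 to 750. That agrees with the stated figure of more than 80%. A set of 0, 5, 50 and 150 also exceeds 80%, so the power does not identify the top dose.

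**The general formula.** The plan gives no worked ED90 to reproduce, so the algebra is what can be checked. Let m be the maximum dose. Solving d/(ED50 + d) = P·m/(ED50 + m) gives d = P·ED50·m/(ED50 + (1−P)·m), which is the printed general form. It returns exactly 90% of the effect at m when P = 0.9.

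**Putting in m, with P = 0.9:**
- m = 150: ED90 = 135·ED50/(ED50 + 15). For positive ED50 this is always below 0.9 × 150 = 135.
- m = 450: ED90 = 405·ED50/(ED50 + 45).
- Share of the 450 effect reached at the 150-based value: 0.9 × [150/(ED50 + 150)] ÷ [450/(ED50 + 450)] = 0.3·(ED50 + 450)/(ED50 + 150).

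The ED50 values 7.5 to 750 are the five candidates in Section 3.2. The value 1 is the lower end of the range in the power claim. Doses are in µg/kg.

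| ED50 | ED90, m = 150 | ED90, m = 450 | Understated by | Share of 450 effect (should be 90%) |
|---|---|---|---|---|
| 1 | 8.4 | 8.8 | 4% | 90% (89.6%) |
| 7.5 | 45.0 | 57.9 | 22% | 87% |
| 15 | 67.5 | 101.3 | 33% | 85% |
| 30 | 90.0 | 162.0 | 44% | 80% |
| 60 | 108.0 | 231.4 | 53% | 73% |
| 750 | 132.4 | 382.1 | 65% | 40% |

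**Exponential expression.** ED90 = δ·log(0.9·exp(m/δ) + 0.1). At the shell's δ = 100 it is 141.9 with m = 150 and 439.6 with m = 450. At δ = 200 the values are 139.2 and 431.3. Both are about 68% too low.

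**Estimate against interval.** Suppose the ED function uses 450 and the draws use the printed 150. The point estimate exceeds 135 when 405·ED50 > 135·(ED50 + 45), that is 270·ED50 > 6,075, or ED50 > 22.5. Above that value the estimate lies beyond anything a draw with positive ED50 can produce. At a fitted ED50 of 60 the estimate is 231.4, while every such draw is below 135.

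**The case against.** The strongest reply is that the SAP does not hand the calculation to the printed number. The correct general formula stands first on the same line, the item's wording and the shell footnote agree with it, and the ED function is named for the purpose. Only the worked substitution is wrong. A reader might infer that the reported ED90 will be too low. The documents do not support that, because they do not show that 150 would enter the function. What remains open is the interval, where ED has to be calculated draw by draw and the printed closed form is the obvious thing to code.

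The size also varies. "Far too low" would be right for moderate or large ED50s but not for a very potent curve: at an ED50 of 1 the two versions differ by about 4%.

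The exponential expression may never be used. Section 8.1 limits model selection in the MOD step to hyperbolic Emax, sigmoidal Emax or linear. The shell does list exponential contrasts in the MCP step, and the Section 15 sentence that introduces the two models is cut by redaction, so the intended role cannot be read.

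Finally, the reach is narrow. A reader might infer damage to the primary result or to the whole MOD table. Neither follows: the MCP test and its type I error, the pairwise estimates, the MMRM, the ED50, the target dose, the asymptotic ED90 and the effects at each dose do not use max(doses). All of these limits stand. None of them makes the printed expression right.

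**Conclusion.** The inconsistency is real and lies in unredacted text: a pre-specified formula contradicts its own definition and the table it feeds. Its effect is conditional. It needs the printed 150 to be coded, a significant MCP test and stage 4 to be initiated, and it then touches only the ED90 row. Under those conditions the Emax ED90, or its interval, is understated by 22% to 65% across the candidate ED50s and cannot exceed 135. If estimate and draws use different constants, the interval could exclude the estimate once the fitted ED50 is above 22.5.

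This rests on 450 being the highest dose analysed, as the shells and the interim plan show, and on positive ED50 in the draws. It should be fixed, but it does not threaten the trial's main conclusion.

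**What to change.** In Section 15, item 2, delete both substituted expressions that contain 150 and keep the general forms. Add one sentence: max(doses) is the highest dose in the analysed data (450 according to the shells), and the same value is used for the ED-function point estimate and for every simulation draw. Tying it to the data also covers any change to stage 4 after the interim analysis. In the same edit, reconcile the number of draws, which is 10,000 in Section 15 and 100000 in footnote 6 of shell Table 14.2.1.2.1.

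The cost is one line of SAP text and one constant in the program. The change concerns the analysis formula only and implies nothing about dosing.
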